## 7.1.2 Life-threatening

An adverse event or suspected adverse reaction is considered *life threatening* if, in the view of either the investigator or sponsor, its occurrence places the patient or subject at immediate risk of death. It does not include an adverse event or suspected adverse reaction that, had it occurred in a more severe form, might have caused death.

# 7.2 Adverse Event Reporting

The study period during which AEs must be reported begins after randomization and ends three months following surgery or until start of other tumor-directed therapy, whichever is earlier. For subjects on the re-treatment arm, AE reporting begins once the subject is confirmed eligible and is thus enrolled on the re-treatment arm.

After the Day 8 visit, all subjects will be followed by chart review and/or telephone contact every month for three months, or until an off-study criterion is met, to collect survival, CSF cytology if clinically indicated, brain and spine MRIs, toxicity assessment and disease status information.

[figure not shown]
If the patient experiences an AE considered to be **related** to study products, then the patient will be followed until resolution of that AE or until the patient is off study (whichever is earlier).

The Investigator will assign attribution of the possible association of the event with tozuleristide or the Canvas system or both, or to neurosurgery, and this information will be entered into the appropriate case report form. The Investigator must also comply with all reporting requirements to their institutional Data and Safety Monitoring Committee and Institutional Review Board (IRB).

# 7.3 SAEs and Expedited Reporting

Blaze Bioscience has requirements for the expedited reporting of SAEs that meet specific criteria of the appropriate regulatory authorities; therefore, all appropriate parties must be notified as soon as possible and within 24 hours of the investigator becoming aware of the event. The procedures for reporting all SAEs, regardless of causal relationship, are as follows:

- In the case of a SAE, information should be recorded on a SAE Report Form and faxed or emailed to the contacts below.
- Initial SAE notification can be done by email but must be with 24 hours

Blaze Bioscience may request additional information from the investigator to ensure the timely completion of accurate safety reports.

The investigator must take all therapeutic measures necessary for resolution of the SAE. Any medications necessary for treatment of the SAE must be recorded in the concomitant medication section of the subject's CRF.

An SAE may qualify for reporting to regulatory authorities if the SAE is considered to have a possible causal relationship to the study product and is unexpected/unlisted based upon the current Investigator's Brochure. In this case, all investigators will receive a formal notification describing the SAE.

Where this is required by local regulatory authorities, and in accordance with the local institutional policy, the investigator should notify (in writing) the IRB of SAEs according to local guidelines.

### 7.4 Toxicity Management

#### 7.4.1 Definitions

The grading of AEs and abnormal laboratory values will be based on the guidelines provided in the CTCAE Version 5.0.

For the purpose of monitoring toxicities, the baseline value is defined as the last value prior to randomization. This value must be obtained from the laboratory appointed to analyze study samples. All management is based on changes from this value.

#### 7.4.2 Guidance for Dose Modification or Discontinuation of Treatment

[figure not shown]
Dosing will be stopped if suspected adverse drug reactions, changes in vital signs, or clinical laboratory results are observed, and these changes pose a significant health risk.

If the patient experiences an AE considered to be related to study products, then the patient will be followed until resolution of that AE or until they are off study (whichever is earlier).

# 7.4.3 Warnings and Precautions

There are no specific warnings or precautions for tozuleristide.

For further information regarding warnings and precautions with the study product, please refer to the current Tozuleristide Investigator's Brochure.

# **8.2** Investigational Device Information

Refer to Section 5.2 for information of the Canvas system. Detailed information is also provided in the current Canvas Imaging System Investigator's Brochure.

### 9 EVALUATION CRITERIA

# 9.1 Independent Safety Monitoring Committee (SMC)

The SMC's responsibilities are to:

- Review the protocol and plans for data safety and monitoring;
- Conduct regular interim and final evaluation of study safety including aggregate and individual subject data related to safety, data integrity, and overall conduct of the study;
- Consider factors external to the study when relevant information becomes available, such as scientific or therapeutic developments that may have an impact on participant safety, scientific integrity, or the ethics of conducting the study;
- Protect the safety of the study subjects;
- Review and evaluate ad hoc safety issues concerning the study at the request of Blaze Bioscience;
- Make recommendations to Blaze Bioscience concerning continuation, termination, or other modifications of the study based on the observed beneficial or adverse effects of the study; and
- Operate according to the procedures described in the all procedures of the SMC.

# 9.2 Central Radiology

• All MRI processes for central radiology are detailed in the study reference manual.

## 9.3 Central Pathology

[figure not shown]
 Primary tumor tissue specimens and equivocal tissue specimens will be required for central pathology assessment of presence or absence of tumor. Central pathology samples will be requested after completion of site final pathology report for standard clinical management. "Other biopsy" tissue specimens, if obtained, will also be evaluated by central pathology.

[figure not shown]

• Central pathology will be blinded to treatment allocation and fluorescence data but will have access to routine pathology data (gross and microscopic pathology reports), images and/or slides for microscopic evaluation, and molecular/genetic data.

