### Study Design

Randomized, blinded (central pathology, central fluorescence assessment and central radiology), multi-center study of a single dose of tozuleristide in subjects with pediatric primary CNS tumors; intraoperative imaging will be performed with the Canvas system.

Two Arms (randomized 1:10):

- Arm 1 (no drug treatment): ~9% of subjects

  Subject not injected with tozuleristide and undergoes standard of care neurosurgery
- Arm 2 (tozuleristide treated): ~91% of subjects
   Subject injected with tozuleristide and undergoes standard of care neurosurgery

[figure not shown]
During the surgical procedure, and once the tumor has been accessed, the Canvas system, which is attached to the surgical microscope, will be used to capture and display intraoperative *in situ* images (white light and fluorescence) of the region from which surgical specimens for biopsy or excision will be collected. All clinical decision-making regarding tissue resection will be made based on the routine neurosurgical practices, and tissue resection will take place under normal light conditions in line with best clinical practices.

[figure not shown]
In addition to primary tumor biopsy, regions of equivocal nature (uncertain if tumor or not tumor) will be identified before fluorescence in the operating room is determined. Each clinical site will have an imaging operator who is not operating nor involved with patient surgical management. The imaging operator will ensure white light and fluorescent images are captured and will assess and document fluorescence status (none, weak, or strong) by looking at the Canvas monitor. The operating surgeon will assign presumed status of equivocal tissue (tumor/not tumor) and indicate the region to be biopsied and imaged by pointing at it with an instrument under the microscope.

[figure not shown]

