Tozuleristide and the Canvas system are intended as an aid to surgical decision-making. As such, when a region of interest in the brain/spine is noted to be fluorescent, it is always the surgeon's decision whether to biopsy/resect if safe to do so. A 1:10 randomization scheme will be used to help reduce selection bias, and aid in the integrity of the blinded pathology, and radiology assessments. Subjects will be randomly assigned to either Arm 1 (no tozuleristide treatment) or Arm 2 (tozuleristide treated) after enrollment. Fluorescence assessment by the imaging operators will be used in the primary efficacy analyses. Subjects who are randomized to Arm 1 or Arm 2 and need to undergo an additional surgery for their brain tumor will be eligible to receive tozuleristide without being subject to randomization. Subjects must meet all study eligibility requirements and re-consent for study prior to re-enrollment for open-label treatment with tozuleristide (retreatment). The pathology assessment of tissue as tumor or not tumor, for both arms, will be done by a centralized and independent panel of pathologists without knowledge of fluorescence status or treatment arm (blinded pathology). Post-operative centralized and independent MR image assessment , for both arms, will be done without knowledge of fluorescence status, treatment assignment, or surgical assessment (blinded radiology).

Number of Subjects	Approximately 114 subjects are planned.
Duration of Therapy	For subjects in Arm 2, tozuleristide will be administered as a single intravenous (IV) bolus dose at least one hour and no more than 36 hours before planned start time of surgery.
Duration of Follow up	Three months post-surgery
Duration of study	Approximately 52 months
Study Drug(s)	

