## 4.1.2 Blinding

This is a randomized, blinded (central pathology, central fluorescence assessment, and central radiology) study. A 1:10 randomization scheme will allocate ~9% of subjects to a no study drug standard of care neurosurgery arm. This will help to reduce subject selection bias and expectation of fluorescence in the operating room.

The pathology assessment of tissue as tumor or not tumor, for both arms, will be done by a centralized and independent panel of two pathologists without knowledge of fluorescence status, surgeon's designation of tissue status or treatment arm (blinded pathology).

[figure not shown]

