3.2 Central Pathology

The pathology assessment of a tissue specimen (primary, equivocal or other) as tumor or not tumor, for both arms, will be performed by a centralized and independent panel of pathologists without knowledge of fluorescence status or treatment arm (blinded pathology).

[figure not shown]

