4 STUDY ENDPOINTS

4.1 Primary Efficacy Endpoints

[figure not shown]
The primary efficacy endpoints are:

- 1. Ratio of sensitivity of tozuleristide fluorescence in equivocal tissue biopsies from subjects with fluorescence-positive tumors compared to the sensitivity of surgical designation from the same biopsies under white light conditions
- 2. Ratio of specificity of tozuleristide fluorescence in equivocal tissue biopsies from subjects with fluorescence-positive tumors compared to the specificity of surgical designation from the same biopsies under white light conditions
- 3. Sensitivity of tozuleristide fluorescence to detect tumor in equivocal tissue biopsies from subjects with fluorescence-positive tumor
- 4. Specificity of tozuleristide fluorescence to detect tumor in equivocal tissue biopsies from subjects with fluorescence-positive tumor

Fluorescence positivity for the primary endpoints is defined as weak or strong fluorescence as determined by the imaging operator fluorescence assessment based on displayed fluorescence signal and exposure setting.

Confidential Page 11 of 37

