8.11.1 Primary Efficacy Endpoints

8.11.1.1 Primary Analyses of Sensitivity and Specificity

The primary efficacy analyses will be based on Group 2 in the full analysis population (Section 7). Each of the 4 sets of statistical hypotheses will be tested at two-sided 5% level (Section 5) using the repeated measures log-linear model specified in this section. Each equivocal tissue specimen from Group 2 that is determined to be either tumor positive or tumor negative by central pathology, and has an image operator assessment and/or a surgeon assessment will be used in the analysis.

[figure not shown]
Confidential Page 22 of 37

[figure not shown]
Confidential Page 23 of 37

[figure not shown]
Confidential Page 24 of 37

Confidential Page 25 of 37

Confidential Page 26 of 37

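### Does the shorter blinding list in Protocol 9.3, the abstract and SAP 3.2 let the central pathologists see the surgeon's call?

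*Protocol*

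**What the plan says.** The visible text states the central pathology blind in four places.

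- Protocol 4.1.2 (Blinding) names three items: fluorescence status, the surgeon's view of the tissue, and arm. The last two appear as "designation of tissue status or treatment arm (blinded pathology".
- The protocol abstract (Study Design) names two: "panel of pathologists without knowledge of fluorescence status or treatment arm (blinded pathology".
- Protocol 9.3 names two and then grants access to site material: "Central pathology will be blinded to treatment allocation and fluorescence data but will have access to routine pathology data (gross and microscopic pathology reports". The same sentence adds images and/or slides and molecular data. On timing, 9.3 says: "Central pathology samples will be requested after completion of site final pathology report for standard clinical management".
- SAP 3.2 names two: "without knowledge of fluorescence status or treatment arm (blinded pathology".

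The abstract places the surgeon's call in the operating room: "The operating surgeon will assign presumed status of equivocal tissue (tumor/not tumor) and indicate the region to be biopsied". SAP 4.1 makes that call the comparator; endpoint 1, for instance, is the sensitivity of fluorescence "compared to the sensitivity of surgical designation from the same biopsies under white light conditions". SAP 8.11.1.1 restricts the primary analysis to specimens "determined to be either tumor positive or tumor negative by central pathology", and SAP 13.1 builds both paired tables on that central classification.

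**The concern.** A reference standard should be read without knowledge of either test that it judges. Three of the four statements protect against knowledge of fluorescence but are silent on the surgeon. One of them, 9.3, is the section that describes what the panel receives: it pairs a two-item blind with access to completed site reports. The surgeon's call already exists when the tissue reaches pathology. The abstract's next sentence, on central radiology, does list the surgical assessment among the blinded items, which can make its absence from the pathology sentence look deliberate.

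If the surgeon's call reached the panel and swayed it, the reference would drift towards the comparator. The surgeon's apparent accuracy would rise, that of fluorescence would tend to fall, and the ratios in endpoints 1 and 2 would tend to shrink. A real advantage over white-light judgement could be missed.

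**Working it through.** **Step 1. Compare the four statements.**

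| Place | Fluorescence | Arm | Surgeon's call |
|---|---|---|---|
| Protocol 4.1.2 | blinded | blinded | blinded |
| Protocol abstract | blinded | blinded | not mentioned |
| Protocol 9.3 | blinded | blinded | not mentioned |
| SAP 3.2 | blinded | blinded | not mentioned |

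No cell says that the panel may see the surgeon's call. The four statements can all be obeyed at once, and doing so means obeying 4.1.2.

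**Step 2. Look for a route.** For 9.3 to defeat 4.1.2, the site reports would have to contain the surgeon's tumor/not-tumor designation. The abstract shows that designation as a study assignment made in surgery. No visible passage sends it to the site pathologist or puts it in a gross or microscopic report. What the site report does convey is the local pathologist's reading, which is neither of the two tests being compared. If a report did carry the surgeon's impression, 4.1.2 would require it to be withheld.

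**Step 3. Consider the silence on masking and read order.** The public copy has undisplayed material in 4.1.2, 9.3 and SAP 3.2, and the protocol numbering passes from 9.3 to 9.5. Absence of a step in that text cannot be taken as absence from the plan.

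**Step 4. Size, if a leak did occur.** The documents give no figure to reproduce, and every input here is an assumption: tumor prevalence 0.70, fluorescence sensitivity/specificity 0.80/0.70, surgeon 0.70/0.60, independent errors. Let L be the share of the surgeon's wrong calls that the reference adopts.

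- Surgeon wrong on tumor: 0.70 × 0.30 = 0.21. Surgeon wrong on non-tumor: 0.30 × 0.40 = 0.12.
- Sensitivity ratio = [0.56 − L(0.21 × 0.80) + L(0.12 × 0.30)] / [0.49 + 0.12L] = (0.56 − 0.132L) / (0.49 + 0.12L).
- Specificity ratio = [0.21 − L(0.12 × 0.70) + L(0.21 × 0.20)] / [0.18 + 0.21L] = (0.21 − 0.042L) / (0.18 + 0.21L).

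| L | Sensitivity ratio | Specificity ratio |
|---|---|---|
| 0 | 0.56/0.49 = 1.143 | 0.21/0.18 = 1.167 |
| 0.05 | 0.5534/0.4960 = 1.116 | 0.2079/0.1905 = 1.091 |
| 0.10 | 0.5468/0.5020 = 1.089 | 0.2058/0.2010 = 1.024 |

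At L = 0.05 the share of reference calls altered is (0.21 + 0.12) × 0.05 = 1.65%. The specificity ratio reaches 1.00 when 0.21 − 0.042L = 0.18 + 0.21L, so L = 0.03/0.252 = 11.9%. With error correlation 0.3 that break-even is 15.5%. At 85% prevalence it is 6.1% (independent errors), and at 50% prevalence 19.2%.

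A second model lets a share q of all central reads follow the surgeon, with fluorescence assumed at 0.85/0.75, the surgeon at 0.70/0.60 and prevalence from 0.50 to 0.85. The sensitivity ratio goes from 1.214 at q = 0 to between 1.128 and 1.169 at q = 0.10. The specificity ratio goes from 1.250 to between 0.968 and 1.150.

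**Step 5. Direction.** Both ratios fell in all 5,728 feasible sets of one grid of assumed inputs. In a wider grid (all four accuracies 0.5 to 0.9, error correlation up to 0.9, 5% adoption) at least one ratio rose in 220 of 7,028 sets, or 3.1%. Downward is therefore usual but not guaranteed. It is also largely built in, because the model moves the reference only towards the surgeon.

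**The case for a change.** The best argument for acting is that people work from the section that concerns them. A pathologist handed 9.3 and a folder of site reports could follow 9.3 to the letter without being told that the surgeon's opinion is off limits. The comparator in two co-primary endpoints deserves the same explicit protection as fluorescence, the radiology sentence shows that the sponsor knew how to write it, and Step 4 shows that a small leak could matter. Repeating the third item costs almost nothing.

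What stands is that the wording differs between sections and the missing item is an important one. What does not stand is the step from there to a faulty reference standard. The argument needs the panel to be run without regard to the protocol's own Blinding section, and it needs site reports to carry a study variable that no passage puts there. The SAP sentence describes the design for analysts and does not direct how the panel reads slides. Nor is a locked read before site reports are opened a free addition. Section 9.3 expressly chooses to give the panel routine pathology context, and nothing in the documents shows that per-specimen calls would be better without it.

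**Conclusion.** No change to the plan follows. Protocol 4.1.2 already withholds the surgeon's designation from the central panel, and the three shorter statements are incomplete summaries of that rule that do not override it. Following the documents as written gives a reference standard blinded to both tests, which is L = 0 in the illustration and leaves the ratios untouched. Copying the third item into the other sections would be housekeeping; it would alter no estimate, test or sample size.

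The figures for a leak show only what would happen if 4.1.2 were breached. Their inputs are assumed throughout, and the decisive one, how often pathologists reading slides would adopt a surgeon's error, has no basis in the documents. The usual direction would be against tozuleristide, so the main risk would be lost power and not a false claim of superiority.

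This conclusion rests on two assumptions: that 4.1.2 governs panel conduct, and that site reports either omit the surgeon's call or have it withheld as 4.1.2 requires. Evidence that reports carrying the designation reached the panel unmasked would reopen the point as a matter of trial conduct.

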# 9.5 Protocol Endpoint Assessment Committee (PEAC)

Roles and responsibilities are outlined in the PEAC study charter.

#### 10 STATISTICAL CONSIDERATIONS

## 10.1 Study Design/Endpoints

[figure not shown]
The study design is presented in Section 3.

# 10.1.1 Primary Endpoints

The primary efficacy endpoints are:

- 1. Ratio of sensitivity of tozuleristide fluorescence in equivocal tissue biopsies from subjects with fluorescence-positive tumors compared to the sensitivity of surgical designation from the same biopsies under white light conditions
- 2. Ratio of specificity of tozuleristide fluorescence in equivocal tissue biopsies from subjects with fluorescence-positive tumors compared to the specificity of surgical designation from the same biopsies under white light conditions
- 3. Sensitivity of tozuleristide fluorescence to detect tumor in equivocal tissue biopsies from subjects with fluorescence-positive tumor
- 4. Specificity of tozuleristide fluorescence to detect tumor in equivocal tissue biopsies from subjects with fluorescence-positive tumor

## **10.1.2** Secondary Endpoints

[figure not shown]
The secondary efficacy endpoints are:

Study endpoints related to the safety objective:

- 1. All reported adverse events (AEs) will be graded according to the National Cancer Institute's Common Terminology for Adverse Events (NCI CTCAE, Version 5.0)
- 2. SAEs
- 3. AE attribution of relatedness to tozuleristide and/or Canvas system (related vs. unrelated).
- 4. Laboratory parameters
- 5. ECG parameters
- 6. Vital signs

[figure not shown]
#### 10.2 Statistical Analysis Plan

In general, descriptive statistics will be provided for all study endpoints. Descriptive statistics will include number of subjects, mean, standard deviation, median, and range (minimum, maximum) for continuous variables, and frequencies and percentages for categorical variables. Statistical tests will be performed at either a one-sided significance level of 2.5% or a two-sided

Version Date: 28 Oct 2021

significance level of 5%. All confidence intervals (CIs) will be constructed at a two-sided 95% confidence level.

In addition, data collected after re-treatment will be listed and will not be included in the efficacy and safety analyses.

### **10.2.2** Analysis Populations

[figure not shown]
The full analysis population (FAP) for efficacy analyses will consist of all subjects who

[figure not shown]
- 1. meet all eligibility criteria
- 2. undergo neurosurgery and

3. have central pathology tumor assessment and imaging operator fluorescence assessment of equivocal tissue specimens obtained from the first neurosurgery on study.

Study subjects in the full analysis population will be classified into four treatment groups:

- **Group 1** (Arm 1): subjects who do not receive tozuleristide, regardless of fluorescence outcomes and tumor diagnosis
- **Group 2** (Arm 2 Fluorescent): subjects who receive tozuleristide, have at least one fluorescence-positive study tissue specimens of any type (primary, equivocal and other) based on imaging operator fluorescence assessment, and the subject's central pathology consensus diagnosis is tumor, ambiguous, or not definitive

The safety analysis population will consist of all subjects who receive any amount of tozuleristide or receive neurosurgery prior to any re-treatment. Safety data collected in the retreatment portion of the study will be listed separately.

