## 10.2.5 Analyses of Primary Efficacy Endpoints

The primary efficacy analyses will be based on Group 2 in the full analysis population (Section 10.2.2). The four sets of statistical hypotheses will be evaluated by assessing the statistical significance of the co-primary endpoints.

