7 ANALYSIS POPULATIONS

[figure not shown]
The full analysis population (FAP) for efficacy analyses will consist of all subjects who

[figure not shown]
Confidential Page 16 of 37

- 1. meet all eligibility criteria,
- 2. undergo neurosurgery, and
- 3. have central pathology tumor assessment and imaging operator fluorescence assessment of equivocal tissue specimens obtained from the first neurosurgery on study.

Subjects in the FAP will be classified into 4 groups:

- Group 1 (Arm 1): subjects who do not receive tozuleristide, regardless of fluorescence outcomes and tumor diagnosis
- Group 2 (Arm 2 Fluorescent): subjects who receive tozuleristide, have at least one fluorescence-positive study tissue specimens of any type (primary, equivocal, and other) based on imaging operator fluorescence assessment, and the subject's central pathology consensus diagnosis is tumor, ambiguous, or not definitive

The FAP will be the primary analysis population for all efficacy analyses, summaries, and listings.

The safety analysis population (SAF) will consist of all subjects who receive any amount of tozuleristide or receive neurosurgery prior to any re-treatment. The SAF will be used for all safety data summaries and listings.

Confidential Page 17 of 37

The all-subject population (ASP) is defined as all subjects who sign informed consent. The ASP will be used for screen failure summaries and listings.

The intent-to-treat (ITT) population is defined as all subjects who are randomized. The ITT population will be used for disposition summaries, protocol deviations, and listings.

No subjects will be excluded from any analysis populations due to protocol deviations.

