8.6 Subject Accountability

Subject accountability will be summarized for the ITT population. Subjects who discontinue tozuleristide prematurely and the reason for tozuleristide discontinuation will be summarized for Arm 2. Subjects who withdraw from the study and the reason for

Confidential Page 19 of 37

study discontinuation will be summarized by treatment arm. The number of subjects who do not undergo surgery will also be summarized by treatment arm.

The number of screen failures and the reason for screen failure will be summarized as a percentage of the all-subject population.

The number of subjects in each analysis population (Section 7) and the reason for excluding from the analysis population will be summarized as a percentage of the all-subject population by treatment arm.

Informed consent (including protocol version), screen failure, eligibility and randomization data will be listed.

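### Entry to Group 2, the set for all four primary endpoints, depends partly on the fluorescence reads being scored: relative to dosed full-analysis subjects with the same diagnosis criterion, pooled sensitivity cannot fall and pooled specificity cannot rise

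*Protocol*

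**What the plan says.** Group 2 (Protocol 10.2.2, SAP 7) contains full-analysis subjects who meet three conditions. They received tozuleristide; their central pathology consensus diagnosis is tumor, or was left ambiguous or not definitive; and they "have at least one fluorescence-positive study tissue specimens of any type (primary, equivocal and other) based on imaging operator fluorescence assessment". The full analysis population itself requires subjects to "have central pathology tumor assessment and imaging operator fluorescence assessment of equivocal tissue specimens obtained from the first neurosurgery on study".

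The index test uses the same reader. SAP 4.1 says: "Fluorescence positivity for the primary endpoints is defined as weak or strong fluorescence as determined by the imaging operator fluorescence assessment".

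Protocol 10.2.5 and SAP 8.11.1.1 both base the primary analyses on Group 2. The protocol adds: "The four sets of statistical hypotheses will be evaluated by assessing the statistical significance of the co-primary endpoints". SAP 8.11.1.1 scores each Group 2 equivocal specimen that has a definite central pathology result and "has an image operator assessment and/or a surgeon assessment will be used in the analysis".

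The endpoint wording (Protocol 10.1.1, SAP 4.1) limits the endpoints to subjects whose tumor is fluorescence-positive. The objectives (Protocol 1.1, SAP 2.1) carry no such condition.

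On accounting, SAP 8.6 states: "The number of subjects in each analysis population (Section 7) and the reason for excluding from the analysis population will be summarized". Two of the four groups, the hypotheses, the sample-size basis and most of SAP 8.11 are not shown in the public text.

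**The concern.** An accuracy estimate is easiest to interpret when the set of subjects is fixed without using the result under test. Here a weak or strong read on an equivocal specimen both counts as a test positive and can bring its subject into the analysis. In the extreme case, a subject has one scored specimen and it is also the only fluorescent one. That subject contributes 100% sensitivity if the specimen is tumor and 0% specificity if it is not, by construction.

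The entry rule is also wider than the endpoint wording. A fluorescent equivocal or other specimen is enough even if the primary tumor specimen is dark, and even if pathology calls the fluorescent specimen not tumor.

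What is at stake is interpretation. A surgeon does not know beforehand whether a dosed patient's tissue will fluoresce, so the Group 2 result alone does not describe accuracy in a dosed patient.

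**Working it through.** **The plan's own figures.** The text gives about 114 subjects randomized 1:10. 114/11 = 10.4 and 114 × 10/11 = 103.6, which agree with the stated 10 and 104. No expected sensitivity, specificity, power or number of specimens per subject is shown, so there is no accuracy figure to reproduce.

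**Direction (pooled counts).** Take as comparator the dosed full-analysis subjects with a qualifying diagnosis. A subject left out for no fluorescence has only negative operator reads, so the scored specimens that leave are false negatives (x of them) or true negatives (y of them).

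- Sensitivity: TP/(TP+FN−x) ≥ TP/(TP+FN).
- Specificity: (TN−y)/(TN−y+FP) ≤ TN/(TN+FP).
- Sensitivity ratio, (a+b)/(a+c) from the SAP 13.1 table: the specimens that leave come from cells c or d, so with both reads on every specimen the ratio cannot fall.
- Specificity ratio, (g+h)/(f+h): no fixed direction. Suppose Group 2 has 66 fluorescence and 47 surgeon true negatives (66/47 = 1.404), and 10 fluorescence true negatives were left out. If the surgeon called 5 of those 10 not tumor, the comparator ratio is 76/52 = 1.462. If the surgeon called all 10 not tumor, it is 76/57 = 1.333.

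In 4,000 simulated trials of 30 dosed subjects with the diagnosis criterion held fixed, sensitivity fell in 0, specificity rose in 0 and the paired sensitivity ratio fell in 0. The specificity ratio fell in 3,551 and rose in 359. Assumed settings included 1 to 4 equivocal specimens per subject and 80% dye uptake.

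**Specimens with one read.** SAP 8.11.1.1 also admits these, and then the sensitivity ratio can move the other way. With fluorescence 8/20 and surgeon 10/12 the ratio is 0.480. Dropping one specimen missed by both gives 8/19 and 10/11, a ratio of 0.463.

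**Size of the circularity alone.** All inputs are assumptions: sensitivity and specificity 0.80, 65% of equivocal specimens tumor-positive, one primary specimen with positivity p, m equivocal specimens, and independent reads.

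- P(an equivocal specimen is positive): q = 0.65×0.80 + 0.35×0.20 = 0.59.
- A positive specimen always stays in Group 2. A negative one stays with probability s = 1 − (1−p)(1−q)^(m−1).
- Group 2 sensitivity = 0.80/(0.80+0.20s); specificity = 0.80s/(0.80s+0.20).
- Share entering only through an equivocal specimen = (1−p)(1−(1−q)^m); share left out = (1−p)(1−q)^m.

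| m | p | s | Sensitivity | Specificity | Equivocal-only entry | Left out |
|---|---|---|---|---|---|---|
| 1 | 0.70 | 0.700 | 0.80/0.940 = 0.851 | 0.560/0.760 = 0.737 | 18% | 12% |
| 1 | 0.80 | 0.800 | 0.80/0.960 = 0.833 | 0.640/0.840 = 0.762 | 12% | 8% |
| 2 | 0.80 | 0.918 | 0.80/0.984 = 0.813 | 0.734/0.934 = 0.786 | 17% | 3% |
| 2 | 0.95 | 0.980 | 0.80/0.996 = 0.803 | 0.784/0.984 = 0.797 | 4% | 1% |

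Under the same independence assumption, each further unscored specimen multiplies the chance of being left out by a factor below 1, so the shift shrinks.

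**How a primary-specimen entry rule behaves.** Assume 20% of subjects have no uptake; sensitivity 0.80 with uptake and 0.15 without; false-positive rate 0.20 and 0.15; primary positivity 0.80 and 0.15. Sensitivity in all dosed is 0.8×0.80 + 0.2×0.15 = 0.670. Let the surgeon also have 0.670, so the ratio in all dosed is 1.00. With a fluorescent primary required, sensitivity is (0.8×0.80×0.80 + 0.2×0.15×0.15)/(0.8×0.80 + 0.2×0.15) = 0.5165/0.670 = 0.771, a ratio of 1.15. Applying the formula above by uptake class, Group 2 gives 0.670/0.8235, 0.670/0.8641 and 0.670/0.8902 for m = 1, 2 and 3, that is ratios of 1.21, 1.16 and 1.12. With three specimens the primary-based subset lies further from the all-dosed value than Group 2 does.

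**The case against.** The strongest reply is that the endpoints openly restrict to fluorescing tumors. A conditional quantity is not wrong because it differs from an unconditional one. That stands: most of the gap in the non-uptake example reflects a declared choice. It does not cover the part of the rule that lets a scored specimen open the gate.

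Second, the circularity may be small. With primary positivity of 0.80 or more, the sensitivity shift is at most 1.3 points with two equivocal specimens and at most 0.5 with three. The larger figures need one equivocal specimen and many dark primaries, and the model leaves out the other specimens that also count for entry. This stands too.

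Third, the missing text may already hold an all-dosed analysis, and SAP 8.6 already counts populations and reasons for exclusion. So a reader should not infer that no such analysis is planned. What the visible text of SAP 8.6 does not give is the route of entry to Group 2 within the full analysis population.

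A reader might also infer that specificity cannot rise against all dosed subjects. The documents do not support that. Group 2 also drops subjects with a non-tumorous diagnosis (SAP 13.2), whose fluorescent specimens are false positives. With assumed counts, suppose Group 2 has 66 true negatives among 94 tumor-negative specimens (0.702). Adding 2 true negatives from all-negative subjects and 16 fluorescent specimens from non-tumor subjects gives 68/112 = 0.607, so Group 2 is higher. When the simulation above included non-tumor diagnoses (8%, assumed) in the comparator, specificity rose in 229 of 4,000 trials.

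**Conclusion.** The point holds with a defined comparator. Group 2 is selected partly by the index test's own result. Against dosed full-analysis subjects meeting the same diagnosis criterion, pooled sensitivity cannot fall, pooled specificity cannot rise, and the fully paired sensitivity ratio cannot fall. The specificity ratio can move either way. These directions are exact for pooled counts; the weighting in the repeated-measures model is not shown.

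The size is unknown. Under the stated assumptions it runs from about 5 points of sensitivity and 6 of specificity (one equivocal specimen, primary positivity 0.70) to 0.3 points of each (two specimens, 0.95).

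A reader might infer an inflated chance of a false trial success. The documents do not support that: specificity moves against the product, and the decision rule across the four co-primary endpoints is not shown. Nor is the restriction to fluorescing tumors itself an error. This is worth changing because the supportive analyses are cheap and show whether the effect is negligible.

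**What to change.** Keep Group 2 as the primary set and leave the primary analysis unchanged.

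1. SAP 8.11.1.1, unless text not shown already does so: repeat the four analyses in all dosed Arm 2 full-analysis subjects with a qualifying diagnosis, regardless of fluorescence, and report them beside the Group 2 results.
2. SAP 8.11.1.1: add a sensitivity analysis in which entry rests on a fluorescence-positive primary-tumor specimen, which is not itself scored. Leave out and count subjects with no primary-specimen read. State that this removes the circularity but not the restriction effect, and that it is not always closer to the all-dosed value.
3. SAP 8.6: report how many dosed full-analysis subjects are left out of Group 2 for no fluorescence and how many enter only through an equivocal specimen.

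The cost is SAP wording, two repeated analyses and one count table from reads already collected. The downside is a little more analysis work and an all-dosed sensitivity that will probably look less favourable.
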